## **14. Data & Safety monitoring:**

Laboratory data, such as hematology and serum chemistry data will be tabulated by dosage group. Summary statistics for changes from baseline will be presented. Hemodynamic measurements will be described using univariable descriptive statistics (mean median, etc.); observed values and changes from baseline will be summarized.

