| Exclusion criteria                 | 
 
1. History of serious adverse event related to ambrisentan administration.
 
2. History of ambrisentan exposure within 48 hours of the study.
 
3. Presence of pulmonary venous obstruction.
 
4. Treatment with cyclosporin
 
5. Any of the following – as determined by the attending physician 
 
a. Significant hemodynamic instability
 
b. Sepsis.
 
c. Need for ECMO support.
 
 
 
6. Renal failure defined as serum creatinine <math>></math> 2 times higher than the upper limit of normal.
 
7. Liver dysfunction defined as alanine aminotransferase or aspartate aminotransferase <math>></math> 3 times higher than the upper limit of normal.
 
8. Thrombocytopenia defined as a platelet count <math><</math> 50 000 cells/<math>\mu</math>L.
 
9. Leukopenia defined as white blood cells <math><</math> 2500 cells/<math>\mu</math>L.
 
10. Anemia defined as hemoglobin <math><</math> 8mg/dL
 
11. Atrial hypertension (mean LA pressure <math>></math> 12mm Hg)
 
 |
| Dose Schedule:                     | Once daily oral administration   |
| Estimated Start:                   | Jan 2014   |
| Estimated Finish:                  | Jan 2016   |
| Duration of therapy                | 3 days   |

|                                   |   |
|-----------------------------------|---|
| PK/PD:                     | Blood samples will be obtained at various time points after drug administration. PK parameters will be estimated by non-compartmental analysis using WinNonLin software. PD parameters will include change in hemodynamic endpoints (Fontan pressures, calculated cardiac index, pulmonary vascular resistance and brachial artery flow mediated vasodilation measured by ultrasound) |
| Statistical Consideration: | This protocol has sufficient enrollment to provide pilot safety and PK data and to allow assessment of the hemodynamic effects of ambrisentan on pulmonary vascular resistance and Fontan pressures.  |

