## 2. Purpose of the Study

The purpose of the study is to evaluate the safety, pharmacokinetics (PK) and pharmacodynamics (PD) of ambrisentan in children with single ventricle heart defects that are undergoing Fontan (stage III) surgical palliation. This is a double blind, placebo controlled study. The primary objective of this Phase I/II study is to assess the plasma PK, safety and PD of oral ambrisentan in children with surgically palliated single ventricle heart defects. A secondary objective will be to assess whether ambrisentan improves post-operative outcomes including amount and duration of chest tube drainage and hospital length of stay.

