## 4. Design and Procedures

This is a single-center, randomized, blinded PK study of ambrisentan in children ages  $\geq 24$  months and  $\leq 120$  months with single ventricle anatomy. There will be up to 20 subjects enrolled; 16 will receive ambrisentan and 4 will receive placebo. A small placebo control group is warranted to ensure that any treatment effect is not a result of post-operative improvement. Patients will be enrolled at the time of their routinely scheduled Fontan surgery.

**Initial Dose:** Oral ambrisentan 2.5 – 5 mg, single dose, once daily (nasogastric and gastrostomy tube administration will be considered only when a nasogastric or gastrostomy tube is already in place as part of routine post-operative care). Subjects will be randomized by Investigational Drug Services (IDS) to placebo (n=4) or oral ambrisentan (n=16) using permuted blocks. Subjects will receive either an oral suspension (2.5 or 5mg) or a 5mg tablet depending on their ability to swallow a tablet. To begin to ensure safety, the initial 5 subjects enrolled in the study (at least 4 active drug) will receive a dose of 2.5mg in a liquid suspension prepared by IDS. After enrollment of these subjects we will perform a preliminary PK/safety analysis and evaluate ambrisentan exposure. If the drug is well tolerated (no grade III or greater adverse events) and exposure is less than the target exposure of 500-800ng/mL, then we may increase the dose to 5mg/dL provided via tablet in those able to take a tablet or suspension for all others. If drug exposure is less than 100ng/mL then we will enroll additional study subjects to ensure that at least 16 study subjects achieve adequate drug exposure. If drug exposure is in the target range then we will continue to enroll study subjects to receive the 2.5mg suspension.

As summarized below, study drug will be discontinued for any grade 3 or greater adverse event. If this occurs then IDS will be permitted to unblind the study patient to allow for appropriate adverse event reporting. Drug administration will start on post-operative day #1 with initiation of oral feeds. Study drug/placebo will be prepared and delivered to the patient bedside by investigational drug services and administered orally. Subjects will continue on study drug for 3 days.

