### **Study Procedures**

1. Record the start and stop time of ambrisentan administration and all concomitant drugs.
2. Hemodynamic evaluation performed during pre-operative cardiac catheterization (obtained as part of usual clinical care), prior to initiation of study drug, and at 0-1,1-6,18-30 and 40-60hrs after administration of the first ambrisentan dose (blood samples will be collected only if central monitoring lines remain or if they can be timed with a routine lab collection)

- a. Record Fontan, common atrial, and systemic arterial pressures from existing central lines that are placed as part of routine post-operative care.
- b. Collect study labs (coincident with scheduled PK levels – see below):
  - i. plasma samples for biomarkers (endothelin 1 [ET1], brain natriuretic peptide [BNP]).
- c. Record oxygen saturation from routinely collected arterial and venous blood gases.
- 3. PK blood samples (500 µL, up to 7 per patient) and pressure measurements will be obtained at baseline and at 1–2, 3–4, 5–6, 8–12, 12–16, 24, and 48 hours post-initial drug administration.
- 4. Adverse events will be collected during and for 1 month after the last study drug administration. Results will be tabulated by organ system.
- 5. Physical examination will be performed within 24 hours after administration of study drug and once daily during study enrollment.
- 6. Record all AEs and SAEs.
- 7. Record all concomitant medication administered 24 hours after administration of study drug.
- 8. Up to 4 scavenge samples will be obtained from the clinical laboratory from samples collected in the 24 hours following ambrisentan administration. Scavenged samples are left over heparinized plasma samples from these children that are collected from the clinical laboratory prior to discarding.

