### **PK Sampling**

A limited PK sampling scheme will be employed such that no more than 3000 µl of blood is obtained.

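### The final analysis neither links pressures to time-matched drug levels nor contrasts them by arm, so it cannot separate a drug effect from post-operative recovery

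*Combined protocol and SAP*

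**What the plan says.** Section 2 makes PD part of the main aim: "The primary objective of this Phase I/II study is to assess the plasma PK, safety and PD of oral ambrisentan". The synopsis defines PD by hemodynamics: "PD parameters will include change in hemodynamic endpoints", namely Fontan pressures, cardiac index, pulmonary vascular resistance and flow-mediated vasodilation.

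Section 4 sets the allocation ("16 will receive ambrisentan and 4 will receive placebo") and the reason for the control arm: "A small placebo control group is warranted to ensure that any treatment effect is not a result of post-operative improvement".

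Section 10, Study Procedures, item 3 puts PK samples and pressures on one schedule: "and pressure measurements will be obtained at baseline and at 1–2, 3–4, 5–6, 8–12, 12–16, 24, and 48 hours post-initial drug administration".

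The analysis text is short. Section 13 gives general descriptive statistics and non-compartmental PK parameters. Section 14 gives, for hemodynamics: "Hemodynamic measurements will be described using univariable descriptive statistics (mean median, etc.); observed values and changes from baseline will be summarized". It names no grouping for these summaries, although the laboratory data are to be tabulated by dosage group. Section 5 mentions a preliminary PK/PD analysis after the first 5 subjects, for dose adjustment and without a method. Sections 4 and 13 describe that same look as PK/safety or PK only.

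**The concern.** Pressures after a Fontan operation can be expected to change with recovery alone. A change from baseline in treated children therefore mixes drug effect and recovery, and Section 4 recognises this. Two kinds of information could separate them: the difference between arms, and the relation of pressure to drug level at the same clock time. The plan specifies an analysis for neither. Left so, the PD part of the primary objective would be reported as before/after summaries that cannot be attributed to the drug, and any later model would be chosen after the data are seen. That matters because the result depends heavily on how time is modelled.

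**Working it through.** **No figure to reproduce.** The documents state no alpha, power, effect size or SD for hemodynamics. Only 16 + 4 = 20 can be checked, and it adds up. Everything below is illustrative, with a two-sided 5% level assumed.

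**1. Pairs available.** Section 10 allows up to 7 PK samples of 500 µL: 7 × 500 = 3500 µL. Its PK Sampling paragraph says "no more than 3000 µl of blood is obtained", and 3000 / 500 = 6. So about 6 concentration–pressure pairs per child is a reasonable ceiling.

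**2. Precision of the arm contrast alone** (one summary value per child).
- SE = SD × √(1/16 + 1/4) = 0.559 SD.
- 95% CI half-width = 2.101 × 0.559 = 1.17 SD (t, 18 df).
- Power for a 1 SD difference is 40%; 80% power needs about 1.66 SD.

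**3. Simulations in mm Hg.** Assumptions: between-child SD 2, random trend SD 1 per 24 h, reading SD 1.5, peak CV 50%; readings at 0, 1.5, 3.5, 5.5, 10 and 24 h; drug effect 1 mm Hg at typical peak. Runs that modelled elimination used the 7.6 h half-life in Section 5. The slope model has categorical time and placebo concentrations set to zero. Ranges are across separate simulations.

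| True drug effect | Slope: estimate | Slope: power | Arm contrast: power |
|---|---|---|---|
| None | 0 | 4–6% (type I error) | – |
| Direct, follows concentration | 1 | 41–53% | 16–21% |
| Sustained 1 mm Hg | 0.37–0.42 | 10–12% | 24–27% |
| Delayed, equilibration rate 0.1/h | 0.28 | 7% | 7% |

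In further runs the slope's advantage shrank as the effect lagged: 27% against 12% at a 1 h half-delay, 12% against 9% at 3 h, and none at 6 h.

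**4. Cross-check by the normal formula,** power ≈ Φ(effect/SE − 1.96). The SE of the slope was 0.52–0.60 and of the arm difference about 0.80.
- Direct, slope: Φ(1/0.60 − 1.96) = Φ(−0.29) = 39% to Φ(1/0.52 − 1.96) = Φ(−0.04) = 48%.
- Sustained, arm: Φ(1/0.80 − 1.96) = Φ(−0.71) = 24%.
- Sustained, slope (0.40, SE 0.56): Φ(0.71 − 1.96) = Φ(−1.25) = 11%.

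These agree broadly with the table.

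**5. Why the form of time must be fixed in advance.** Modelling time as linear when recovery is curved raised the false-positive rate of the slope to 16%. In a separate simulation (total SD 1, pressures falling 1 SD over 48 h from recovery alone), leaving time out and using active children only biased the slope by about +0.6 SD, with 85–96% false positives. With time effects and placebo children included, the rate was 4–6%.

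That separate simulation also gave 84–96% power for the slope against 21–28% for the arms, at 1 SD for about 650 ng/mL. Its arm comparator did not use a pre-dose reading, so I do not rely on it for the size of the gain.

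**The case against.** *This is a pilot of up to 20 children, so description is enough.* The synopsis calls it pilot for safety and PK, and Section 12 looks ahead to a multi-center PK study, so descriptive summaries are defensible and should stay. But the synopsis also promises an assessment of hemodynamic effects, and PD is in the primary objective. Section 13 does list a 95% CI among its descriptive statistics. Even if that is read as applying to hemodynamics by arm, it would give two separate intervals, not the difference.

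*A PK/PD analysis is already planned.* A reader might infer that the plan never joins the two at all; Section 5 does not support that. What it offers, however, is an interim look at 5 children without a method, which does not cover the final data.

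*The model may do worse than the weak contrast it is meant to support.* This stands. The documents say nothing about onset of effect. If the effect is sustained or delayed, the slope is attenuated by 58–72% or so, and a prediction at 500 or 800 ng/mL would be misleadingly small. This is why the arm contrast has to sit beside it.

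*Pairs will be missing.* This also stands in part. Pressures come from existing central lines, and children may move to the floor for doses 2 and 3. Section 10 item 2 lists different hemodynamic windows (0–1, 1–6, 18–30 and 40–60 h), and the text does not say whether the 24 h and 48 h readings precede the next dose. A mixed model tolerates incomplete series but cannot restore lost late readings.

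**Conclusion.** The concern holds as a gap in the final analysis: paired data are scheduled, no planned analysis uses the pairing, and none delivers the separation for which the placebo arm was included.

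Four stronger readings are not supported. The data are not discarded; they are collected and could be modelled later. PK/PD alone is not the primary objective, since safety belongs to it too. The power figures are not plan versus fix, because Section 14 plans no hemodynamic test; they compare two possible additions. And a concentration model does not reliably make up for 4 placebo children: even in its favourable case power is about 40–50% for 1 mm Hg, and it can fall below the arm contrast. The two estimates also measure different things (an average arm difference and a change per typical peak), so comparing interval widths directly would mislead.

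All sizes rest on assumed SDs, complete pairs and, in several of the runs, a known covariance, which is optimistic. What does not depend on these values is that a before/after summary cannot tell drug from recovery. In all simulations the time-adjusted slope kept its error rate near 5%.

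**What to change.** Keep the descriptive summaries. In Sections 13 and 14 add two analyses, labelled exploratory:

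- (a) The active-versus-placebo difference in change in pressure from the pre-dose reading, with 95% CI, from a repeated-measures model with categorical time.
- (b) A linear mixed model of pressure on time-matched plasma concentration (placebo = 0), with categorical time shared by both arms, the pre-dose reading included and a random child effect. Report the slope with 95% CI. Give any predicted change at 500 and 800 ng/mL only with the statement that it assumes a direct effect that follows concentration.

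Reconcile the item 2 and item 3 measurement windows in Section 10, and the sample count with the blood cap. State whether the 24 h and 48 h readings come before the next dose. Levels must be linkable to pressures by study code once blinding no longer matters, since Section 5 has identifiers removed before levels are released.

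Cost: two models, with no added patients or blood. Downsides to state in the plan: attenuation under a sustained or delayed effect, possible confounding if sicker children clear the drug more slowly, and missing late pairs. Model (b) covers pressures only. Cardiac index, pulmonary vascular resistance and flow-mediated vasodilation are not stated to be measured at the PK times.

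### Hemodynamic results get only univariable summaries of observed values and changes, with no estimate of the arm difference adjusted for the pre-dose reading, although a 16 v 4 split makes chance baseline imbalance likely

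*Combined protocol and SAP*

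**What the plan says.** The combined protocol and SAP describes the hemodynamic analysis in two clauses of section 14: "Hemodynamic measurements will be described using univariable descriptive statistics (mean median, etc", and "observed values and changes from baseline will be summarized". The synopsis puts the pharmacodynamic measure in terms of change: "PD parameters will include change in hemodynamic endpoints". No section names a covariate, a model, a test or an estimate of the difference between arms. Section 14 tabulates laboratory data by dosage group but does not say how hemodynamic values are grouped.

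On design, section 4 states: "There will be up to 20 subjects enrolled; 16 will receive ambrisentan and 4 will receive placebo". Allocation uses permuted blocks, and no stratification on hemodynamics is mentioned. The same section gives the reason for the control arm: "A small placebo control group is warranted to ensure that any treatment effect is not a result of post-operative improvement".

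On timing, section 10 (Study Procedures) has: "Hemodynamic evaluation performed during pre-operative cardiac catheterization (obtained as part of usual clinical care), prior to initiation of study drug, and at" four windows after the first dose (0–1, 1–6, 18–30 and 40–60 hours). There are therefore two candidate baselines, one from the pre-operative catheterization and one taken after surgery but before the first dose. Section 14 does not say which it means.

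**The concern.** The stated purpose of the placebo arm can be met only by comparing arms. With four placebo children, the arms may well start at different levels by chance. A reader who compares the planned summaries by arm will carry that difference into the apparent drug effect.

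A change score subtracts the whole baseline difference, which is too much whenever the correlation between baseline and follow-up is below 1. An arm that happens to start high then appears to improve. An observed value subtracts none of the difference, so that arm appears worse. The two tables can point different ways, and the plan has no rule for choosing between them. Precision may also be lost, although the reading that would recover it is already scheduled.

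**Working it through.** **The plan's own figure.** The only figure to reproduce is the count: 16 + 4 = 20, which agrees. The plan gives no effect size, SD, alpha or power.

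**Inputs.** Arm sizes of 16 and 4 come from section 4. Assumed, because the documents give none: normal data, the same SD at both times, and a baseline-to-follow-up correlation rho varied from 0.3 to 0.95. All results are in between-child SD units.

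**Chance imbalance.** The SD of the baseline difference between arms is k = √(1/16 + 1/4) = √0.3125 = 0.559. The probability that it exceeds 0.5 SD in either direction is 2 × [1 − Φ(0.5/0.559)] = 37%; for 1 SD it is 7%. With 10 v 10 the SD would be 0.447 and the first probability 26%.

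**What an imbalance does.** Suppose the ambrisentan arm starts 0.559 SD higher, which is one SD of the imbalance distribution.
- Arm difference in change: shifts by −(1 − rho) × 0.559.
- Arm difference in observed values: shifts by +rho × 0.559.

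**Precision.** The standard error of the arm difference is k√v, where:
- observed value: v = 1, so SE = 0.559 at every rho;
- change score: v = 2(1 − rho);
- ANCOVA with estimated slope: v = (1 − rho²) × (1 + 1/(20 − 4)) = (1 − rho²) × 1.0625.

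At rho 0.5, for example, the change score has v = 1.000 and SE 0.559. ANCOVA has v = 0.75 × 1.0625 = 0.797 and SE 0.499.

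| rho | Shift, change | Shift, observed | SE change | SE ANCOVA | Variance, ANCOVA v change | Mean 95% CI half-width, change → ANCOVA |
|---|---|---|---|---|---|---|
| 0.3 | −0.39 | +0.17 | 0.661 | 0.550 | −31% | 1.37 → 1.14 |
| 0.5 | −0.28 | +0.28 | 0.559 | 0.499 | −20% | 1.16 → 1.04 |
| 0.7 | −0.17 | +0.39 | 0.433 | 0.412 | −10% | 0.90 → 0.86 |
| 0.8 | −0.11 | +0.45 | 0.354 | 0.346 | −4% | 0.73 → 0.72 |
| 0.88 | −0.07 | +0.49 | 0.274 | 0.274 | 0% | 0.57 → 0.57 |
| 0.9 | −0.06 | +0.50 | 0.250 | 0.251 | +1% | 0.52 → 0.52 |
| 0.95 | −0.03 | +0.53 | 0.177 | 0.180 | +4% | 0.37 → 0.37 |

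The variance ratio simplifies to (1 + rho) × 17/32, so break-even is at rho = 32/17 − 1 = 0.88. A simulation of 100,000 trials per correlation matched these standard errors and supplied the half-widths. In it, the arm difference in change correlated with the baseline imbalance at −0.50 (rho 0.5) and −0.39 (rho 0.7). For ANCOVA that correlation was about 0.

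**What adjustment cannot do.** By the normal approximation, at two-sided 5% and 80% power, the detectable difference in observed values is (1.960 + 0.842) × 0.559 = 1.57 SD. With ANCOVA it is 1.40 SD at rho 0.5 and 1.15 SD at rho 0.7.

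**The case against.** The strongest reply is that section 14 contains no arm contrast to criticise. It is a descriptive plan for a small study that the synopsis presents as giving pilot safety and PK data. On this view, choosing ANCOVA over change scores is secondary to the larger gap, that no treatment-effect estimate is defined. This narrows the point without removing it. Section 4 gives the placebo arm a purpose that needs the contrast, and the fix supplies the missing estimate.

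Four stronger readings are tempting and should not be adopted.
- *The plan reports raw change only.* It does not: section 14 also summarises observed values. This is no rescue, because those values carry the imbalance in the other direction.
- *The change score is biased.* Over repeated randomization its arm difference is unbiased. The error is conditional on the imbalance that actually occurs.
- *The correlation can be taken from the pediatric study in section 5.* Its figures (55 ± 18 to 45 ± 20 mm Hg, p = 0.04) imply rho of about 0.57 only if a paired t test was run on all 16 children. There, SD of change = (10/2.2485) × √16 = 17.79, and rho = (324 + 400 − 316.5)/720 = 0.566. Section 5 states neither the test nor the number paired. The same arithmetic gives about 0.70 with 12 pairs, 0.80 with 9 and 0.90 with 6. Those children also had pulmonary hypertension rather than a recent Fontan operation. Hence the range used here.
- *Adjustment would make the comparison adequate.* It would not, as the detectable differences show.

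It also stands that a common slope would be estimated mostly from the active arm and could hardly be checked in four placebo children.

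**Conclusion.** The point holds as a modest, nearly free improvement that should be made. The plan has no baseline-adjusted arm estimate, its control arm calls for one, and neither planned summary removes a chance imbalance that is likely with 16 v 4.

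The imbalance result depends on the arm sizes in section 4. Section 13 instead speaks of up to 50 subjects enrolled and receiving drug, and other arm sizes would change the figures. The precision result depends on an assumed correlation: the gain over change scores is material at 0.3 to 0.7, small at 0.8, absent near 0.88 and slightly negative above that. The calculations also assume complete readings. Section 10 takes pressures from existing lines, so the numbers may be smaller at later windows.

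**What to change.** Add to section 14, in substance:

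> Baseline is the post-operative reading taken before the first dose, not the pre-operative catheterization value. For each hemodynamic measure with a pre-dose value, the ambrisentan minus placebo difference and its 95% CI will be estimated at each post-dose window from a linear model of the post-dose value on arm and pre-dose value. These estimates are exploratory. Observed values and changes from baseline will be tabulated by arm as supporting information, with the number of children contributing.

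Reconcile the enrolment figures in sections 4 and 13 so that the arm sizes are fixed.

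The cost is a few sentences and one residual degree of freedom (20 − 3 = 17 instead of 20 − 2 = 18). No new data are needed. Children without a pre-dose reading drop out of the model, but they have no change from that baseline either. The report should say that the slope comes mostly from the active arm and that the intervals remain wide.
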